## 16 STATISTICAL / ANALYTICAL ISSUES

#### 16.1 Handling of Dropouts or Missing Data

All data will be used to their maximum possible extent but without any imputations for missing data.

#### 16.2 Interim Analysis

A data monitoring committee (DMC) consisting of two external investigator advisors and specified Clovis personnel was to meet approximately quarterly after the first patient was enrolled to review the efficacy and safety data.

A detailed description of the composition, roles and responsibilities, and functioning of the DMC is provided in the DMC Charter.

## **17** SAFETY ANALYSIS

The safety analyses will be performed using the Safety Population.

#### 17.1 Adverse Events

The severity of the toxicities will be graded according to the NCI CTCAE whenever possible. Treatment-emergent AEs are defined as AEs with an onset date on or after the date of first dose of lucitanib until the date of the last dose of protocol-specified treatment plus 28 days. AEs will be considered treatment-emergent if all or part of the date of onset of the AE is missing and it cannot be determined if the AE meets the definition for treatment-emergent.

The number and percentage of patients who experienced treatment-emergent AEs for each system organ class and preferred term will be presented by treatment group. Multiple instances of the treatment-emergent AEs in each system organ class and multiple occurrences

of the same preferred term are counted only once per patient. The number and percentage of patients with at least one treatment-emergent AE will also be summarized by treatment group. Separate tables will present the following by cohort:

- All treatment-emergent AEs
- Treatment-emergent AEs by CTCAE grade
- Treatment-related, treatment-emergent AEs by CTCAE grade
- Grade 3 or greater treatment-emergent AEs
- Treatment-related, treatment-emergent AEs
- Serious treatment-emergent AEs
- Serious treatment-related, treatment-emergent AEs
- Treatment-emergent AEs of Grade 3 or higher
- Treatment-related, treatment-emergent AEs of Grade 3 or higher
- Treatment-emergent AEs with an outcome of death
- Treatment-related, treatment-emergent AEs with an outcome of death
- Treatment-emergent AEs leading to discontinuation of study drug
- Treatment-related, treatment-emergent AEs leading to discontinuation of study drug
- Treatment-emergent AEs resulting in interruption of study drug
- Treatment-related, treatment-emergent AEs resulting in interruption of study drug
- Treatment-emergent AEs resulting in study drug dose reduction
- Treatment-related, treatment-emergent AEs resulting in study drug dose reduction
- Treatment-emergent AEs resulting in interruption or reduction/delay of study drug
- Treatment-related, treatment-emergent AEs resulting in interruption or reduction/delay of study drug
- Treatment-emergent AEs resulting in interruption, reduction, or discontinuation of study drug
- Treatment-related, treatment-emergent AEs resulting in interruption, reduction, or discontinuation of study drug

The incidence of treatment-emergent AEs will be summarized by relationship to lucitanib using "treatment-related" and "not treatment-related" categories. If a patient experiences multiple occurrences of the same AE with different relationship categories, the patient will be counted once in the relationship category of treatment-related.

If a patient experiences multiple occurrences of the same AE with different intensity toxicity grades, the patient will be counted once for the maximum (most severe) toxicity grade. AEs with a missing intensity will be presented in the summary table with a toxicity grade of "Missing." For each toxicity grade, the number and percentage of patients with at least one

treatment-emergent AE of the given grade will be summarized.

Non-treatment-emergent AEs (pretreatment and post treatment) will be presented in the data listings.

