5.1.2 Treatment Period

Lucitanib will be administered once daily and swallowed with water (see [Section 7.3](#)). Patients should take lucitanib at approximately the same time each day, on an empty stomach, at least 2 hours before and 2 hours after a meal (fasting window is a total of four hours). Treatment with lucitanib is continuous but cycles will be defined as 28 days in duration. Dosing will be delayed or reduced according to protocol-specified toxicity criteria (See [Section 7.4](#)). Protocol-specified treatment will continue until there is clinical tumor progression or unacceptable toxicity.

Patients will undergo serial assessments for anti-tumor efficacy, drug safety, and PROs. Tumor scans will be acquired by the investigative site and evaluated locally for patient treatment decisions. Electronic copies of tumor scans will be uploaded to a central radiological vendor and held for review, if deemed necessary. Sparse blood sampling for POPPK analyses will be conducted in all patients treated with lucitanib. Serial blood sampling for PD evaluation will be conducted. Local laboratories will be used for standard hematology and chemistry tests. Echocardiogram (ECHO)/multiple-gated acquisition (MUGA) will be done locally. ECGs will be stored and may be analyzed centrally. Patients will be asked to self-monitor their BP at least two times per week and instructed to contact the study site in the event of a BP reading equal or above 160 mmHg systolic and/or greater than 100 mmHg diastolic (see [Section 9.5.1.3](#)).

Patients with SD or better after their Cycle 6 scan will continue to have tumor scans every 12 ± 1 weeks until tumor progression. After discontinuation of protocol-specified treatment, subsequent specific anticancer therapy used at the investigator's discretion will be recorded. Patients will be encouraged to undergo an optional post-treatment tumor biopsy at time of progression and before subsequent-line therapy is initiated.

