11.2.5.2 Adverse Events

AE coding will be performed using the Medical Dictionary for Drug Regulatory Activities. The severity of the toxicities will be graded according to the NCI CTCAE Version 4.03 criteria whenever possible. Treatment-emergent AEs are defined as AEs with an onset date on or after the date of first dose of lucitanib until the date of the last dose of protocol-specified treatment plus 28 days. AEs will be considered treatment-emergent if all or part of the date of onset of the AE is missing and it cannot be determined if the AE meets the definition for treatment-emergent.

The number and percentage of patients who experienced treatment-emergent AEs for each system organ class and preferred term will be presented by individual dose group and by dose groups combined. Multiple instances of the treatment-emergent AEs in each system organ class and multiple occurrences of the same preferred term are counted only once per patient. The number and percentage of patients with at least one treatment-emergent AE will also be summarized by individual dose group and by dose groups combined.

Separate tables will present the following by cohort:

- All treatment-emergent AEs
- Treatment-emergent AEs by CTCAE Version 4.03 grade
- Grade 3 or greater treatment-emergent AEs
- Treatment-related, treatment-emergent AEs
- Serious treatment-emergent AEs
- Serious treatment-related AEs
- Treatment-emergent AEs with an outcome of death
- Treatment-emergent AEs leading to discontinuation of lucitanib
- Treatment-emergent AEs resulting in interruption, reduction, or delay of lucitanib

The incidence of treatment-emergent AEs will be summarized by relationship to lucitanib using “treatment-related” and “not treatment-related” categories. If a patient experiences multiple occurrences of the same AE with different relationship categories, the patient will be counted once as a relationship category of treatment-related.

If a patient experiences multiple occurrences of the same AE with different intensity toxicity grades, the patient will be counted once for the maximum (most severe) toxicity grade. AEs with a missing intensity will be presented in the summary table with a toxicity grade of “Missing.” For each toxicity grade, the number and percentage of patients with at least one treatment-emergent AE of the given grade will be summarized.

Non-treatment-emergent AEs (pre-treatment and post-treatment) will be presented in the data listings.

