11.3 Sample Size Considerations

Up to 200 patients will be enrolled.

A total of at least 80 patients in the 10 mg arm is sufficient to reliably estimate the median PFS and 6 month PFS rate in these heavily pre-treated patients. An observed median PFS greater than 4 months or a 6-month PFS rate of at least 40% will be sufficient to consider the 10 mg dose group worthy of further study. Therefore, with at least 80 patients treated at 10 mg, the width of the 90% confidence interval for the 6 month PFS rate will be less than $\pm 10\%$, so that if the observed 6 month rate is 50% then the lower limit on the confidence interval will be greater than 40%.

The treatment effect in Cohort C (biomarker negative sub-group) is not expected to be as large as in Cohorts A and B; however, the same target of 40% will be used to evaluate Cohort C. With 40 patients, the width of the 90% confidence interval for the 6 month PFS rate will be less than $\pm 15\%$, so that if the observed 6 month rate is less than 25% then the upper limit on the confidence interval will be less than 40%, which is evidence that subsequent studies of 10 mg should exclude biomarker negative patients.

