## **4** GENERAL ANALYSIS CONSIDERATIONS

Due to significant changes to the study design throughout the study, all summaries of data will be presented by initial study drug dose level (10 mg, 15 mg) regardless of a patient's enrollment into study cohorts A, B, and C. Initial dose groups will be referred to as treatment groups (10 mg, 15 mg). An overall column combining all patients from both treatment groups will be included in the data summaries, where applicable.

Quantitative variables will be summarized using descriptive statistics (N, mean, standard deviation, median, minimum, and maximum) and/or frequency and percentages for medically relevant categories. Categorical variables will be presented using frequencies and percentages. Exact 95% confidence intervals may be presented for frequencies.

All data will be used to their maximum possible extent but without any imputations for missing data.

All statistical analyses will be conducted with the statistical analysis software (SAS®) System, Version 9.3 or higher.

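### Adverse events are shown only as crude percentages over windows whose length depends on treatment duration, so groups treated for different times can differ at equal risk

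*SAP*

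**What the plan says.** SAP 17.1 gives the AE summary measure: "The number and percentage of patients who experienced treatment-emergent AEs for each system organ class and preferred term will be presented by treatment group". Repeats "of the same preferred term are counted only once per patient". The treatment-emergent window opens at first dose and runs "until the date of the last dose of protocol-specified treatment plus 28 days". Protocol 11.2.5.2 uses the same count, which "will be presented by individual dose group and by dose groups combined".

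The length of treatment is not fixed. Protocol 5.1.2: "Protocol-specified treatment will continue until there is clinical tumor progression or unacceptable toxicity".

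The grouping is not settled. SAP 17.1 introduces its list of AE tables with "Separate tables will present the following by cohort", whereas SAP 4 says "all summaries of data will be presented by initial study drug dose level (10 mg, 15 mg) regardless of" the cohort a patient was enrolled in.

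Exposure is summarised elsewhere: duration, total dose, mean daily dose and days dosed in SAP 9; cycles, reductions and interruptions in Protocol 11.2.5.1. Neither document plans an exposure-adjusted AE rate, a time-to-first-AE analysis or an incidence over a fixed period.

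**The concern.** A once-per-patient percentage is a cumulative proportion over that patient's own window. Here the window closes 28 days after a stopping point that is itself an outcome, since treatment ends mainly for progression or toxicity. If groups differ in time on treatment, their percentages differ even when the risk per month is the same.

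Unequal exposure is plausible on the plan's own account. Protocol 3.7 says 15 mg was hard for many patients to sustain. Protocol 11.3 says: "The treatment effect in Cohort C (biomarker negative sub-group) is not expected to be as large as in Cohorts A and B". Protocol 11.2.1 also foresees comparing the two dose groups and the FGF subgroups.

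What is at stake is the reading of the safety tables, which serve a secondary objective. A dose group with longer treatment could look more toxic than it is. A higher-risk group that stops sooner could look safer.

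**Working it through.** The documents state no expected AE rate, treatment duration or AE precision, so there is no planned figure to reproduce. What follows is an illustration on assumed inputs.

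**Inputs**
- Tail after last dose: w = 28/30.44 = 0.92 month (SAP 17.1).
- 6-month PFS of 50%, 40% and 25%: figures from Protocol 11.3, where 40% is the target and the other two are conditional illustrations of confidence limits.
- Assumed: exponential treatment time that ends at progression, and a constant first-event hazard h per month, equal in both groups.

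**Formulas**
- Stopping rate: μ = −ln(S6)/6, giving 0.1155, 0.1527 and 0.2310 per month for 50%, 40% and 25%.
- Mean window: 1/μ + w, giving 9.58, 7.47 and 5.25 months.
- Expected crude proportion: 1 − e^(−hw) · μ/(μ + h).
- Example, h = 0.10 and S6 = 50%: 1 − 0.912 × 0.1155/0.2155 = 51.1%.

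**Crude percentage at equal hazard**

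| h per month | S6 50% | S6 40% | S6 25% | Gap 50 v 40 | Gap 50 v 25 |
|---|---|---|---|---|---|
| 0.02 | 16.3 | 13.2 | 9.6 | 3.1 | 6.7 |
| 0.05 | 33.3 | 28.1 | 21.5 | 5.3 | 11.9 |
| 0.10 | 51.1 | 44.9 | 36.3 | 6.2 | 14.8 |
| 0.20 | 69.5 | 64.0 | 55.4 | 5.6 | 14.1 |

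**Dose groups.** Assume mean treatment of 6 months on one dose and 20% or 40% less (4.8 or 3.6 months) on the other. With μ = 1/mean and h from 0.05 to 0.20, the gap is 3.6 to 4.6 points for the 20% shortfall and 7.5 to 10.6 points for the 40% shortfall.

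**The order can reverse.** Suppose 15 mg had 1.5 times the 10 mg hazard (0.075 versus 0.05) and assumed median treatment of 2 versus 4 months (μ = ln 2/median). The crude figures are then 23.3% at 15 mg and 25.9% at 10 mg.

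**Early-onset events.** With 80% of patients susceptible and mean onset at 0.25 month, crude incidence stays between 79.8% and 80.0% for median treatment times from 2 to 8 months.

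**Checking two remedies**
- *Common 84-day window* (L = 84/30.44 = 2.76 months), patients who leave the window counted as event-free: 1 − e^(−hw) + e^(−hw) · h/(h + μ) · [1 − e^(−(h+μ)(L−w))]. At h = 0.10, S6 50% versus 25% gives 22.6% versus 21.4%, so the gap falls from 14.8 to 1.3 points. Over h from 0.02 to 0.20 it is 0.3 to 2.1 points.
- *Exposure-adjusted first-event rate.* For a constant hazard it works: at h = 0.10 with median treatment of 2 versus 4 months, simulation gives 0.0997 versus 0.0998 per patient-month, against crude 29.2% versus 42.2%. For the early-onset event above, with the 5.25- and 9.58-month windows, it gives about 64 versus 38 per 100 patient-months although crude incidence is 80% in both groups. It then creates a gap that is not there.

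**The case against.** The strongest case against runs as follows. The tables are descriptive and no AE test is planned. Exposure is already reported, so a reader can see unequal durations. For dose groups, the comparison the SAP clearly plans, the documents give neither size nor direction: Protocol 3.7 speaks of dose reductions at 15 mg rather than shorter treatment, and Protocol 3.6.1.3 says AEs rarely led to discontinuation, with the commonest causes at 2.3% each. Hypertension, reported in over 80% of patients, can start within days (Protocol 7.4.1).

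All of this stands as a limit on size and weight. It does not remove the point, because separate exposure summaries show that windows differ but not what the percentages would be over equal time.

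Three stronger readings are tempting, and the documents do not support them.
- *The AE tables support the choice of starting dose.* Protocol 3.7 dates the move to 10 mg to mid-2015, on interim data, before this SAP. The Cohort C criterion in Protocol 11.3 uses 6-month PFS, not AEs.
- *50% and 25% are the expected PFS rates.* Protocol 11.3 uses them to show where confidence limits would fall if those rates were observed. The one target is 40%, for both populations.
- *AE tables by cohort are certain.* SAP 4 and SAP 17.1 disagree, and the cohort part of this point depends on how that is resolved.

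**Conclusion.** The point holds as a reporting weakness that is cheap to repair. AEs are displayed by starting dose, and possibly by cohort, only as crude percentages over patient-specific windows. If treatment duration differs between groups, those percentages differ at equal risk for events that accrue over time.

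The size is conditional: 3 to 6 points for 6-month PFS of 50% versus 40%, 7 to 15 points for 50% versus 25%, and 4 to 11 points for an assumed 20-40% shorter mean treatment time on one dose, direction unknown. These rest on exponential treatment times, constant equal hazards and, for the PFS-based figures, treatment that lasts until progression. First-month events are barely affected. The documents give no onset times that would show which AEs arise late.

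**What to change.** In SAP 17.1, before database lock:

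1. Keep the crude tables. Reconcile the by-cohort wording with SAP 4.
2. Add the cumulative incidence of first onset within a common window from first dose, for example 84 days, by starting dose and, if reported, by FGF status. In PK sub-study patients the window starts at the Day -7 dose. Do this for all treatment-emergent AEs, Grade 3 or higher, serious, and named events of interest such as hypertension, proteinuria, hypothyroidism and thrombotic microangiopathy.
3. State in advance whether death or the end of the treatment-emergent window is a competing event or censoring. Censoring would remove the remaining gap in the illustration, but it assumes that stopping is unrelated to AE risk, which is doubtful when toxicity is a reason to stop.
4. Add exposure-adjusted first-event rates only for events that accrue over time, not for early-onset events such as hypertension.
5. Base descriptive between-group statements about harm on the common-window figures, read with the SAP 9 exposure summary. Note that 15 mg starters were later advised to reduce to 10 mg (SAP 2.1); neither summary separates the two doses within that group.

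The cost is a few tables from onset and dosing dates already collected. The common window does not describe later events.

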### **17.2** Clinical Laboratory Evaluations

Clinical laboratory evaluations include variables for hematology, serum chemistry, and urinalysis. Laboratory values will be presented in Systeme International (SI) units. The baseline laboratory value will be defined as the last value prior to or on the day of the first dose of oral lucitanib. The on-treatment period will be defined as the day after the first dose of oral lucitanib to 28 days after the last dose of lucitanib. Laboratory values collected during the on-treatment period will be included in the summary tables. The laboratory values collected after the on-treatment period will only be presented in the data listings.

The summary of laboratory data will include descriptive statistics (N, mean, standard deviation, minimum, median, and maximum) of the maximum, minimum, and last value during the treatment period by treatment group. Summaries using descriptive statistics of the change from baseline to the maximum, minimum, and last value during the on-treatment period will also be presented by treatment group.

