In case of patient presenting with ALT >3 times the ULN concurrent with a total bilirubin >2 times the ULN with no evidence of hemolysis, and an alkaline phosphatase < 2 times the ULN or not available, lucitanib must be stopped permanently.

Abnormal values in AST and/or ALT concurrent with abnormal elevations in total bilirubin, in the absence of other causes of liver injury, are considered potential cases of drug-induced liver injury (potential Hy's Law cases) and as such, should always be considered important medical events. Patients who present that combination of laboratory abnormalities should be evaluated further to definitively determine the etiology of the abnormal laboratory values.

The patient should return to the investigational site and be evaluated as soon as possible, preferably within 48 hours from awareness of the abnormal results. This evaluation should include laboratory tests, detailed history, physical assessment, and the possibility of hepatic neoplasia (metastases) should be considered. In addition to repeating AST and ALT, laboratory tests should include albumin, total bilirubin, direct bilirubin, prothrombin time (PT) and alkaline phosphatase. A detailed history, including relevant information, such as review of ethanol, recreational drug and supplement consumption, family history, sexual history, travel history, history of contact with a jaundiced subject, surgery, blood transfusion, history of liver or allergic disease, and work exposure, should be collected. Further testing for acute hepatitis A, B, or C infection and liver imaging (e.g., biliary tract) may be warranted. All cases confirmed on repeat testing as meeting the criteria mentioned above with no other cause for liver function test (LFT) abnormalities identified at the time should be considered potential Hy's Law cases irrespective of availability of all the results of the investigations performed to determine etiology of the abnormal LFTs.

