11.2.5.3 Clinical Laboratory Evaluations

Clinical laboratory evaluations include the continuous variables for hematology, serum chemistry, and urinalysis. Laboratory values will be presented in Systeme International units. The baseline laboratory value will be defined as the last value prior to or on the day of the first dose of lucitanib. The on-treatment period will be defined as the day after the first dose of lucitanib to 28 days after the last dose of lucitanib. Laboratory values collected during the on-treatment period will be included in the summary tables. The laboratory values collected after the on-treatment period will only be presented in the data listings.

The summary of laboratory data will include descriptive statistics (N, mean, standard deviation, median, minimum, and maximum) of the maximum, minimum, and last value during the on-treatment period by dose group. Summaries using descriptive statistics of the change from baseline to the maximum, minimum, and last value during the on-treatment period will also be given by dose group. Separate listings will be produced for clinically significant laboratory abnormalities (i.e., those that meet Grade 3 or 4 criteria according to CTCAE Version 4.03) by individual dose group and by dose groups combined.

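### SAP 17.2 summarises laboratory variables one at a time, so no planned table counts patients whose ALT and bilirubin rise together as Protocol 7.4.6 describes

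*SAP*

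**What the plan says.** Protocol 7.4.6 contains two liver rules, which are not the same.

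- **Permanent stop.** The trigger is "ALT >3 times the ULN concurrent with a total bilirubin >2 times the ULN with no evidence of hemolysis", together with "an alkaline phosphatase < 2 times the ULN or not available, lucitanib must be stopped permanently". It is specific to ALT and uses multiples of the ULN.
- **Potential Hy's Law case.** This begins with "Abnormal values in AST and/or ALT concurrent with abnormal elevations in total bilirubin", in the absence of another cause of liver injury. It covers AST as well as ALT and gives no multiple. Such cases are described as ("potential Hy's Law cases) and as such, should always be considered important medical events".

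Laboratory abnormalities are a secondary endpoint (Protocol 4.2.2). ALT, AST, total bilirubin and alkaline phosphatase (ALP) all belong to the chemistry panel (Protocol 9.5.1.2). The panel is taken at screening, Cycle 1 Days 1 and 15, Day 1 of every later cycle, and End-of-Study (Protocol Table 4).

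On analysis, SAP 17.2 states: "Clinical laboratory evaluations include variables for hematology, serum chemistry, and urinalysis". Values are shown in SI units. The summary is the number, mean, standard "deviation, minimum, median, and maximum) of the maximum, minimum, and last value during the" treatment period by treatment group, with the same statistics for change from baseline. Protocol 11.2.5.3 opens in much the same way ("Clinical laboratory evaluations include the continuous variables for hematology, serum chemistry, and urinalysis") and adds listings of Grade 3 or 4 abnormalities. SAP 17.2 does not carry those listings over.

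**The concern.** Both rules in 7.4.6 depend on two analytes being abnormal in the same patient at the same time, and the stopping rule is scaled to the ULN. The planned summary is neither joint nor ULN-scaled. SAP 17.2 does not name ALT, AST or bilirubin, but summary statistics of each serum chemistry variable treat them one at a time. There is no threshold count, no rule for what counts as concurrent, and no listing of patients who meet the combined criterion. SAP 17.3 to 17.5 add nothing on this point. The protocol does plan threshold categories for QT and QTc (11.2.5.5), so counting patients beyond a safety limit is not foreign to it.

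The clinical study report could therefore follow the plan exactly and still not say how many patients met the protocol's own liver criterion, or that none did. Two features make pooled SI values harder to read. Tests are run at local laboratories across about 30 to 40 sites. Patients with liver metastases may also enter with AST and ALT up to 5 times ULN, so some can start above the ALT limit.

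**Working it through.** The documents give no figure to reproduce, because the point concerns an analysis that is absent. The check asks whether the planned outputs could recover the count.

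**1. Criterion against output**

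| Needed to apply the stopping criterion | Provided by SAP 17.2 |
|---|---|
| ALT and bilirubin from the same patient at the same time | Each variable summarised separately |
| Multiples of the ULN | SI units |
| ALP below 2 times ULN, or not available | Not linked to ALT or bilirubin |
| Evidence of hemolysis | Not addressed |

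**2. Two patients with the same summaries (assumed values, in multiples of ULN)**

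| Visit | Patient X: ALT, bilirubin | Patient Y: ALT, bilirubin |
|---|---|---|
| 1 | 4.0, 0.8 | 4.0, 2.5 |
| 2 | 1.0, 2.5 | 1.0, 0.8 |
| 3 | 1.0, 0.8 | 1.0, 0.8 |

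For both patients ALT has maximum 4.0, minimum 1.0 and last value 1.0. Bilirubin has maximum 2.5, minimum 0.8 and last value 0.8. Given equal baselines, the changes from baseline also agree. Y has ALT above 3 and bilirubin above 2 at visit 1; X never has both. Every SAP 17.2 output is the same for X and Y, in whatever unit.

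**3. Would separate threshold counts be enough?** If a of n patients exceed the ALT limit and b exceed the bilirubin limit, the number exceeding both lies between max(0, a + b − n) and min(a, b). With assumed counts:

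- n = 200, a = 20, b = 10: from max(0, −170) = 0 to 10.
- n = 80, a = 8, b = 4: from max(0, −68) = 0 to 4.

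Separate counts would not settle the matter either. The joint count has to be made patient by patient.

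**4. Is a case likely to arise?** The documents give no rate, so I assume a true rate p between 0.2% and 2%. The chance of at least one case is 1 − (1 − p)^n.

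- n = 80: 15% to 80%.
- n = 200: 33% to 98%.

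**5. What zero cases would allow the report to say.** The one-sided 95% upper bound with no events is 1 − 0.05^(1/n).

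- n = 80: 3.7%.
- n = 120: 2.5%.
- n = 200: 1.5%.

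The sizes are planning figures: about 80 in Cohort A; 80 plus up to 40 in Cohort C; up to 200 overall. None is the number starting at 10 mg. Cohort C patients enrolled under Amendment 3 were assigned 15 mg, and SAP Section 4 groups patients by initial dose.

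**The case against.** The strongest reply is that these patients would not vanish. A laboratory abnormality that leads to action on study drug is an adverse event (Protocol 10.4). Important medical events may be serious (10.2), and serious events are reported within 24 hours (10.8). Investigators are told to combine findings into one diagnosis where they can (10.6), and 7.4.6 asks for a prompt work-up. SAP 17.1 tabulates serious events and events leading to discontinuation. SAP 17.2 implies that laboratory data listings exist, and a data monitoring committee reviews safety about quarterly. Neither document promises a Hy's Law table, so no commitment is broken.

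Most of this stands, and it rules out some stronger readings that a reader might infer:

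- **That potential liver-injury cases would go unreported, or be scattered across unrelated event terms.** The routes above contradict that. What they lack is identification: events are tabulated by reported preferred term, with no liver-injury category. Attribution also matters. Under 10.3, events clearly related to progression are not reported as serious unless fatal, and 7.4.6 asks investigators to consider hepatic metastases.
- **That averaging hides an extreme ALT.** SAP 17.2 also reports the largest of the patients' maxima, so an outlying ALT could be visible. What cannot be seen is whether bilirubin rose with it.
- **That every important medical event under 7.4.6 meets the stopping rule.** The two definitions differ in analytes, multiples and conditions.

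It is also fair to say that a laboratory table cannot by itself establish drug-induced liver injury. The protocol's definition needs other causes excluded case by case, and its stopping rule needs hemolysis considered. The latter is a practical matter here: Protocol 3.6.1.3 reports serious thrombotic microangiopathy in 14 of 230 pooled patients (6.1%).

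**Conclusion.** The point holds as a reporting gap. No planned table or listing identifies patients with concurrent elevation of ALT or AST and bilirubin, and the planned summaries cannot yield that number. At the assumed counts above, they would leave a range of 0 to 10 among 200 patients, or 0 to 4 among 80. Affected patients may surface in the serious or discontinuation adverse event tables, or in data listings, without being labelled as meeting the criterion.

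This rests on reading SAP 17.2 as variable-by-variable summaries, which its wording supports, and on finding no combined count elsewhere in either document. The rates and counts in the illustration are assumptions; the conclusion does not depend on them. The primary PFS analysis is untouched. The change should be made before database lock, because it lets the report state the result of a safety criterion that the protocol itself sets.

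**What to change.** This concerns reporting only and takes no view on the stopping rule. In SAP 17.2:

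1. Express ALT, AST, total bilirubin and ALP as multiples of the local ULN.
2. Add a table by starting dose counting patients with on-treatment ALT or AST above 3 times ULN, with bilirubin above 2 times ULN, and with both concurrently while ALP is below 2 times ULN or missing. Label it a laboratory screen. Show the protocol's ALT-only criterion separately from the AST-or-ALT version.
3. Define concurrent: same sample, or a stated window.
4. Show separately patients with raised baseline ALT or AST (up to 5 times ULN is allowed with liver metastases) and those with raised baseline bilirubin (the entry limit exempts confirmed Gilbert's disease).
5. List each case with any evidence of hemolysis and any other cause identified.
6. Restore the Grade 3 or 4 laboratory listings from Protocol 11.2.5.3.
7. If no case is seen, give the upper bound using the actual number treated in each starting-dose group.

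The cost is a paragraph of SAP text, one table and one case listing, plus the listings the protocol already specifies. The analytes are already collected. The one practical condition is that local ULNs are available in the dataset.
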